We are proposing a small randomized clinical trial in which 100 substance users will complete the existing Psychotherapy Development Center (PDC) pretreatment assessment battery as well as a novel battery of assays to evaluate cognitive-affective functioning. These batteries will be administered before and after the intervention (cognitive training tasks) to help examine the generalizability of any training effects to related cognitive training tasks (tasks that the participant was not specifically trained on). These related tasks will also help quantify participants' potential responsiveness to treatment and, as such, may help bridge the gap between behavior, mechanism, and treatment.

After completing pretreatment assessments, participants will be randomized to either a (1) cognitive remediation program (training tasks) specifically designed to address cognitive-affective dysregulation or (2) control tasks (verbal fluency tasks). Tasks will be completed twice per week for 4 weeks, after which assessment batteries will be repeated. Finally, we will evaluate real-world behavior and the durability of the training via a one-month follow-up, which will include assessment of substance use as well as the cognitive-affective battery. Our primary Specific Aim will be to evaluate the efficacy of the cognitive-remediation program relative to the control condition control on the indicators of cognitive-affective functioning and substance use, testing the hypothesis that individuals randomized to the cognitive remediation program will demonstrate improved functioning on the cognitive-affective battery as well as reduced substance abuse. We will also explore potential moderators of response to the training, including baseline measures of cognitive-affective function.

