- *Substance Use Calendar*. Self-reports of substance use (cocaine, alcohol, opioids, marijuana, other illicit drugs, and nicotine) are documented at each contact via the Substance Use Calendar. Similar to the Time Line Follow-Back (61), the Substance Use Calendar assesses substance use on a daily basis.
- *State-Trait Anxiety Inventory (STAI)* is a widely-used measure of consistent and transient stress and anxiety (62).
- *Distress Tolerance*. (24, 63, 64) is commonly measured using the Mirror Tracing Persistence Task (65).
- *Shipley Institute of Living Scale* (66) is included as a widely used measure of general intelligence.
- *Balloon Analog Risk Task (BART)* is a computerized measure of risk-taking (67).
- *Five-trial adjusting delay discounting task* is a brief computerized measure of delay discounting (Koffarnus & Bickel, 2014).

Baseline Cognitive-Affective Assessments:

This battery includes three tasks that have been previously used to tap the cognitive-affective processes associated with SUDs and other externalizing disorders.

- *Incentivized n-Back task* includes manipulations of working memory load, response prepotency, and incentivized performance (trial-by-trial feedback using monetary reward and punishment) to examine the integrity of cognitive control functions necessary for successful regulation of behavior. In this task, participants view a series of letters. Participants are instructed to monitor the letters and

Version Date: 03022019

Version 3

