Data will be collected, managed and analyzed through the standard procedures of the PDC as described in detail in the parent grant. Regarding statistical power, [name] previous study using a similar cognitive remediation battery (1) with 55 participants revealed an effect size of $d = .42$ for the malleability of performance on the training, with 92% power. A sample size of 100 will allow us to evaluate the effect of ongoing substance use as a moderator of treatment response at 80% power. We have established that we can recruit and treat a sample of this size in the one-year time allotment of the SOBC supplement. Our rates of end of treatment assessment and follow-up in Center trials is 90% or above, enabling us to conduct true intention to treat analyses with minimal statistical imputation (48, 49, 83). General Linear Modeling will be used to examine change in performance on these tasks over time. Using General Linear Modeling as we have in previous Center-supported studies (10, 37, 49, 57, 84), we will evaluate the extent to which participants who receive cognitive remediation show significantly greater improvement across time in the cognitive-affective assessment battery than those who receive the control training. Additionally, structural equation modeling (SEM) and latent profile analysis (LPA) will be used to examine variable-centered (correlation between measures) versus person-centered (profiles of individuals) alternatives. SEM with maximum-likelihood estimation will be used to test the association between pre-post measures and SUD-related behaviors. LPA, whereby each individual is assigned to a mutually exclusive assay class (i.e. profile) based on a data-driven analytic strategy, will be used to test the association between each individual's pre-post profile and treatment response. Moreover, we will use regression discontinuity analyses compare observations clustered closely on either side of a process-level threshold around a particular intervention. This analysis would allow us to examine the local average treatment effects on pre-post measures in a non-parametric data-driven manner.

Timeline	1	2	3	4	5	6	7	8	9	10	11	12
Recruit 3 participants/week	x	x	x	x	x	x	x	x	x			
Participant 100 completes 4 week treatment											x	
Participant 100 completes 1 month follow-up												x
Data analysis and preparation of reports												x

SECTION II: RESEARCH INVOLVING DRUGS, BIOLOGICS, RADIOTRACERS, PLACEBOS AND DEVICES

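### No week 0 adjustment is specified for the two-arm comparison, and the trial's only power figure (80%, for a substance-use moderator) lacks the inputs and timing needed to check it

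*Protocol*

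**What the plan says.** Protocol section 13 (Statistical Considerations) and the SAP carry the same text. General Linear Modeling is to test whether the remediation arm will "show significantly greater improvement across time in the cognitive-affective assessment battery than those who receive the control training". No covariate is named, and no detectable difference or power is given for this comparison. For data handling and analysis both documents defer to the parent grant, which is not available here.

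The one power figure for this trial concerns a moderator: "A sample size of 100 will allow us to evaluate the effect of ongoing substance use as a moderator of treatment response at 80% power". The other figures in that paragraph (d = .42, 92%) belong to a previous study of 55 participants. On retention the text says: "Our rates of end of treatment assessment and follow-up in Center trials is 90% or above".

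The Statement of Purpose sets the primary hypothesis: participants given remediation "will demonstrate improved functioning on the cognitive-affective battery as well as reduced substance abuse". It also plans to "evaluate real-world behavior and the durability of the training via a one-month follow-up", and to explore moderators, "including baseline measures of cognitive-affective function". Self-reports of use "are documented at each contact via the Substance Use Calendar" (section 4), and the assessment schedule marks the calendar at Week 0, Training, Week 4 and Follow-up. The incentivized n-back is marked at Week 0, Week 4 and Follow-up.

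**The concern.** There are two separate matters.

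**Precision.** The wording points to a change-score or group-by-time test. The week 0 score is already collected, and using it as a covariate normally gives a tighter arm comparison from the same participants. If the plan leaves the choice open, precision may be lost for nothing, and the model can be chosen after the data are seen.

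**The power claim.** The primary aim is the two-arm comparison, yet the only power figure is for a moderator whose size, scale and measurement time are not given. Timing matters most. If ongoing use includes use during training, the assigned arm could change it, and the primary hypothesis says that it should fall. Arm effects at a given level of use would then no longer compare randomised groups.

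**Working it through.** **Inputs from the documents.** N = 100; 80% power for the moderator; retention of at least 90% in other Center trials, so 90 analysed is used as the lower case; d = .42, n = 55 and 92% for the previous study.

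**Assumptions (not in the documents).** Two-sided 5%, 1:1 allocation, equal SDs at week 0 and week 4, and week 0 to week 4 correlation r from .3 to .9.

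**1. The plan's own figures.** The previous study's 92% is reproduced by a one-sided, one-sample or paired t test with n = 55 and d = .42 (92.4%). Two-sided it is 86.4%, and as a 27 v 28 two-group comparison it is 33.3%. This suggests, without proving, that d = .42 is a within-person effect. The 80% cannot be recomputed, because no interaction size, scale or alpha is given. What it requires can be. For a 1-df interaction in a model with four parameters, noncentrality is f² × N, and 80% power needs about 8.0:
- N = 100: f² = 8.01/100 = 0.080 (partial R² = 0.080/1.080 = 0.074)
- N = 90: f² = 8.03/90 = 0.089 (partial R² = 0.089/1.089 = 0.082)

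For a binary moderator split 50:50, by normal approximation, the required difference between the two subgroup treatment effects is (1.96 + 0.84) × 2/√(N × 0.25). That is 1.12 SD of the analysed outcome with 100, and 1.18 with 90.

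**2. Change against baseline-adjusted.** With SD = 1, variance per participant is 2(1 − r) for change and 1 − r² for adjusted. The ratio of adjusted to change is (1 − r²)/[2(1 − r)] = (1 + r)/2. With unequal SDs s0 and s1, change variance minus adjusted variance is (s0 − r·s1)², which is never negative. The ordering therefore does not depend on r or on equal SDs, apart from the one degree of freedom spent on the covariate.

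**3. Detectable two-arm difference, 80% power, 90 analysed.** The difference is √8.02 × 2σ/√90 ≈ 0.597σ, where σ is the square root of the variance in step 2 (noncentral F; results in raw-score SDs).

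| r | change variance | adjusted variance | ratio | 90 adjusted equals, as change | detectable, change | detectable, adjusted |
|---|---|---|---|---|---|---|
| .3 | 1.40 | 0.91 | .65 | 138 | 0.71 | 0.57 |
| .5 | 1.00 | 0.75 | .75 | 120 | 0.60 | 0.52 |
| .7 | 0.60 | 0.51 | .85 | 106 | 0.46 | 0.43 |
| .8 | 0.40 | 0.36 | .90 | 100 | 0.38 | 0.36 |
| .9 | 0.20 | 0.19 | .95 | 95 | 0.27 | 0.26 |

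**4. Timing of the moderator.** The calendar is recorded both at Week 0 and during Training, so either could supply a measure of ongoing use. The text does not choose. The Statement of Purpose says "After completing pretreatment assessments, participants will be randomized to either a (1) cognitive remediation program", which puts pretreatment assessment before allocation. The schedule in section 4, however, marks urn randomization in the Screen column and the battery in the Week 0 column. Whether week 0 data are pre-randomisation therefore needs confirming.

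**The case against.** The strongest reply is that the documents are silent on adjustment; they do not rule it out. General Linear Modeling can carry a baseline covariate, and the parent grant and the cited Center trials may specify one. That stands. A reader might infer that the plan rejects baseline adjustment, or that its comparison is invalid. Neither follows: under randomisation a change or group-by-time test is valid, and the cost is precision only.

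It is also fair that the gain rests on an assumed r. At r = .8 or .9 the detectable difference hardly moves, and no value in the documents excludes such correlations. The table uses two visits, whereas the battery is given at three, so it illustrates the week 4 contrast and not every model the plan might fit.

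A reader might further infer that the 80% is wrong or the trial underpowered. The documents do not support this. The scale of d = .42 for a between-arm test is not given. Read as raw-score SDs with 90 analysed as change, power would run from 38% at r = .3 to 88% at r = .8.

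Nor do the documents say that the moderator is measured after randomisation, since the calendar is also taken at Week 0. And there is no contradiction between the Statement of Purpose and section 13 over moderators, because the baseline measures named in the former are examples and not a closed list.

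What remains is that neither the covariate, the timing nor the inputs to the 80% are written down.

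**Conclusion.** The point holds as one of specification. Adjustment for the week 0 score is not stated. In large samples a change test is never more precise than the adjusted one, and adjustment reduces the number needed by 35/25/15/10/5% at r = .3/.5/.7/.8/.9 (100 minus the ratio in the table). That is worthwhile at low to moderate correlation and minor at high. The 80% is uncheckable, not refuted; it needs f² of about 0.080 to 0.089 at two-sided 5%. The two-arm primary comparison has no power statement at all. The threat to interpretation from a moderator measured after randomisation is conditional on what is meant by ongoing use. The sizes rest on the assumed r, equal SDs, two-sided 5%, 1:1 allocation and, for the detectable differences, 90 analysed; the ordering of the two analyses does not rest on r or equal SDs. This should be fixed, but the design stands.

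**What to change.** Keep N = 100 and amend protocol section 13 and the SAP together.

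1. State that each battery outcome at week 4 is compared between arms with its own week 0 score as covariate, and that the one-month follow-up is analysed the same way as a durability question. This requires naming the outcome taken from each task.
2. Define the substance-use moderator from week 0, pre-randomisation data. Substance use during training and follow-up remains an outcome, compared by randomised arm.
3. Restate the 80% with its interaction size, scale and alpha, and add the detectable two-arm difference. For example, with 90 analysed, two-sided 5%, 1:1 and adjusted, it is 0.57/0.52/0.43/0.36 raw-score SDs at assumed r = .3/.5/.7/.8.
4. Confirm that week 0 assessments precede randomisation, and reconcile the schedule with the Statement of Purpose.

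The cost is wording: no added participants, visits or measurements. The downside is that the stated power may look less favourable once its inputs are shown.

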4. **Research Plan:** Summarize the study design and research procedures using non-technical language that can be readily understood by someone outside the discipline. **Be sure to distinguish between standard of care vs. research procedures when applicable, and include any flowcharts of visits specifying their individual times and lengths.** Describe the setting in which the research will take place.

Overview:

The proposed SOBC supplement project will be conducted at the Substance Abuse Treatment Unit (SATU) and Adult Outpatient Psychiatric Services (IOP) in New Haven. One hundred substance

Version Date: 03022019

Version 3

users will be randomized, via a computerized urn randomization program (55) we have used in multiple previous trials (9, 10, 37, 56, 57) to either the cognitive remediation package or a control condition (computerized verbal fluency tasks), with trainings conducted twice per week for 4 weeks. Training will be conducted as an add-on to the participants' ongoing standard treatment at the clinic.

Several variables will be assessed. Demographic variables will include gender, race, and level of education. Person-specific variables will include type and severity of substance use disorder, personality characteristics, and treatment readiness. Pre- and post-training testing will evaluate change in cognitive-affective targets, with a one-month follow-up period to evaluate both the durability of training effects as well as impact on real-world behaviors (substance use).

This project will benefit the Parent award (P50 DA 0009241) by enabling us to evaluate how individuals with varying levels of these cognitive-affective deficits respond to study interventions and hence inform future projects which could address whether addressing these deficits via cognitive remediation improves response to empirically validated therapies via 'mechanism-matched' cognitive remediation.

Diagnostic and Baseline Assessments:

After providing written informed consent (see Human Subjects), participants will complete the following components of the Parent award (Psychotherapy Development Center, PDC) Core assessment battery to facilitate comparison with ongoing/previous Center studies:

- *Structured Clinical Interview for DSM-5 (SCID)* (58) (59), including antisocial personality disorder.
- The *Brief Symptom Index (BSI)* (60) is a widely used 53-item inventory of psychiatric symptoms.

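### Substance use is one of the two outcome domains in the primary aim, yet the protocol and SAP state no comparison of the randomised arms on it

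*Protocol*

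**What the plan says.** Section 1 of the protocol (Statement of Purpose) gives the primary aim as to "evaluate the efficacy of the cognitive-remediation program relative to the control condition control on the indicators of cognitive-affective functioning and substance use". The hypothesis is that people randomised to remediation "will demonstrate improved functioning on the cognitive-affective battery as well as reduced substance abuse". The same section describes the one-month follow-up as one "which will include assessment of substance use as well as the cognitive-affective battery". The Overview in Section 4 gives that follow-up month two purposes: durability of the training effect, and impact on real-world behaviour, with substance use named as that behaviour.

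The measure is in Section 4, Diagnostic and Baseline Assessments: "Self-reports of substance use (cocaine, alcohol, opioids, marijuana, other illicit drugs, and nicotine) are documented at each contact via the Substance Use Calendar". The assessment schedule places the Calendar at Week 0, during training, at Week 4 and at follow-up, with urine and breath tests at the same points.

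Section 13 of the protocol and the SAP carry the same analysis text. It opens by referring to the standard procedures in the parent grant. It then says "General Linear Modeling will be used to examine change in performance on these tasks over time", and follows with a comparison of remediation and control on improvement in the cognitive-affective battery. Substance-use behaviours come later: "SEM with maximum-likelihood estimation will be used to test the association between pre-post measures and SUD-related behaviors".

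**The concern.** The aim is written as a comparison of two randomised groups in two domains. For use, what is written is a correlation-type analysis across participants, and that answers a different question. People who do better on the tasks may use less in both arms, which gives an association even if training changes nothing about use. Training could also lower use by a route that the tasks do not capture, which gives an arm effect with little association. In neither case does the association recover the randomised effect.

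The substance-use half of the hypothesis could therefore be reported without a pre-specified test. The Calendar covers six substance categories over several periods, and urine and breath results sit beside it. With no measure, window or model fixed, those choices could be made after the data are seen.

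**Working it through.** This is mainly a reading check. The figures at the end only scale what the missing comparison could show.

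**1. The stated analyses, taken in turn** (Section 13 and SAP)

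- General linear model: explicitly remediation versus control. Its outcome is task performance and the cognitive-affective battery.
- Moderator analysis (power sentence): ongoing use modifies treatment response. Such an analysis would ordinarily contain an arm-by-moderator term, but use is the modifier and the outcome is not named.
- SEM: an association of pre-post measures with substance-related behaviours. No arm term is stated.
- Latent profile analysis: relates a person's profile to treatment response, which is not defined.
- Regression discontinuity: contrasts people on either side of a process-level threshold, with pre-post measures as the outcome. This is not a contrast of the randomised arms.

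Of the five, one is written as a comparison of the arms, and its outcome is the battery. None is written as a comparison of the arms on use.

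**2. Does the battery contain the Calendar?** Section 1 lists use and the battery as separate items, in both the hypothesis and the follow-up sentence. Section 4 lists the Calendar among the parent-award core assessments and introduces the other battery under its own subheading: "This battery includes three tasks that have been previously used to tap the cognitive-affective processes". Only one task is described there, so the make-up of the battery is not fully clear. The Calendar is a self-report record rather than a task, however, and is listed elsewhere.

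**3. Does the intention-to-treat sentence supply the comparison?** It says that assessment rates of 90% or above permit intention-to-treat analysis with little imputation. It names no outcome, model or contrast.

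**4. The plan's own power figures.** The only one that involves use is 80% power at N = 100 for use as a moderator. It cannot be reproduced, because no interaction size, alpha, moderator split or outcome is given. Assuming two-sided 5%, 1:1 allocation, a 50/50 moderator split and no covariate gain, the detectable interaction is 2 × (1.960 + 0.842) × √(2/n). That is 1.12 SD with n = 50 per arm and 1.18 SD with n = 45. The other figure (d = 0.42, 55 participants, 92% power) concerns performance on the training and says nothing about use.

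**5. Scale of the missing comparison.** Inputs: N = 100 and 90% assessment (both from the documents), so 50 or 45 per arm. Allocation of 1:1 is assumed, because urn randomisation is stated without a ratio. Two-sided 5% and 80% power are assumed for this comparison. Detectable d = (1.960 + 0.842) × √(2/n):

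- n = 50: 2.802 × 0.200 = 0.56
- n = 45: 2.802 × 0.211 = 0.59

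Baseline adjustment multiplies these by √(1 − ρ²). With ρ = 0.5 (assumed) the factor is 0.866, giving 0.49 and 0.51.

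**The case against.** The strongest reply is that analysis is expressly referred to the parent grant, which may define a substance-use outcome and an arm comparison. This stands as a limit on the point. A reader might infer that no such comparison is planned anywhere, but the documents do not support that. They support only that neither supplied document states one.

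Second, intention-to-treat analysis implies analysis by randomised group, and the sentence that mentions it covers the follow-up, one of whose purposes is substance use. That is suggestive, but a sentence without outcome, model or contrast does not specify a test.

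Third, Section 1 has both batteries given before and after training, so pre-post measures could be read to include the Calendar, and treatment response could be read to mean use. Neither reading can be ruled out, although the SEM sentence sets the measures against the behaviours. Even if both are granted, the SEM, profile and discontinuity analyses are still not written as comparisons of the randomised arms.

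Fourth, this is a small trial meant to lay groundwork, and it could detect only a fairly large effect on use. That bears on how a result should be read and on how severe the gap is. It does not remove use from the stated primary aim.

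**Conclusion.** The point holds for the two supplied documents. One of the two domains in the primary aim has no stated comparison of the arms, and the one analysis that names substance-related behaviours does not estimate the randomised effect. This is more than missing detail, because the text followed literally would answer the use question with an association.

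A reader might go further and call it a fatal flaw, or express it as so many days of use left unresolved. The documents support neither. The unseen parent grant may fill the gap, the data are being collected in any case, and no SD for use is given. The point rests on the wording and on no calculation. I rate it should-fix.

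**What to change.** Add to the SAP one pre-specified intention-to-treat comparison of the randomised arms on one Calendar outcome, for example the proportion of days of use. Adjust it for the same measure before randomisation. Section 1 places randomisation after the pretreatment assessments while the schedule marks it at Screen, so state that the baseline window ends at randomisation.

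Justify the outcome window against the Section 4 Overview, which assigns the one-month follow-up to evaluating impact on use, and show the training period separately. Report the arm effect with a 95% CI. State whether use is co-primary with the battery or ranked after it and, if co-primary, whether both domains must succeed or either suffices. Label the SEM as an association or mechanism analysis. If the parent grant already specifies such a model, state it in the SAP instead.

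The substances counted, variance estimator, look-back length and handling of missing days also need to be fixed in advance. The documents do not dictate any of them, so those choices belong to the investigators.

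The cost is one more model and some SAP wording, with no new visits or data. The drawback is limited power, as shown in the working. If either domain alone could support the aim and alpha is split to 2.5% each, the unadjusted detectable difference rises to (2.241 + 0.842) × √(2/n), about 0.62 SD with 50 per arm and 0.65 SD with 45. A null result should be read from the interval and not reported as no effect.

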Participants will be randomized to one of 2 training conditions, to be completed twice per week over 4 weeks, *in addition* to standard treatment at SATU/IOP, which typically consists of weekly group meetings, case management and random urine toxicology screening. Each training session will be 30-45 minutes (time variability depends on speed of reading instructions and choices made in the tasks). Across all weeks the participant will complete approximately six hours of training.

Control condition. Participants randomized to this condition will complete a computerized verbal flexibility task (Text Twist). An active computer-based control was selected as it provides a rigorous comparison to intervention and will help address concerns that any game-style activities will produce improvements by controlling for computer time and game experiences, as well as non-specific elements such as support, attention, study contact, activation, and motivation. It is possible an active and engaging control condition may produce modest neurocognitive change in some domains, but available data indicate the control condition is not likely to influence the target-specific processes associated with self-regulation (75).

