Targeting Self-regulatory Deficits Through Cognitive Remediation Intervention

NCT03373240

September 1, 2017

Statistical power, data management and analysis

Data will be collected, managed and analyzed through the standard procedures of the PDC as described in detail in the parent grant. Regarding statistical power, [name] previous study using a similar cognitive remediation battery (1) with 55 participants revealed an effect size of $d = .42$ for the malleability of performance on the training, with 92% power. A sample size of 100 will allow us to evaluate the effect of ongoing substance use as a moderator of treatment response at 80% power. We have established that we can recruit and treat a sample of this size in the one-year time allotment of the SOBC supplement. Our rates of end of treatment assessment and follow-up in Center trials is 90% or above, enabling us to conduct true intention to treat analyses with minimal statistical imputation (48, 49, 83).

General Linear Modeling will be used to examine change in performance on these tasks over time. Using General Linear Modeling as we have in previous Center-supported studies (10, 37, 49, 57, 84), we will evaluate the extent to which participants who receive cognitive remediation show significantly greater improvement across time in the cognitive-affective assessment battery than those who receive the control training. Additionally, structural equation modeling (SEM) and latent profile analysis (LPA) will be used to examine variable-centered (correlation between measures) versus person-centered (profiles of individuals) alternatives. SEM with maximum-likelihood estimation will be used to test the association between pre-post measures and SUD-related behaviors. LPA, whereby each individual is assigned to a mutually exclusive assay class (i.e. profile) based on a data-driven analytic strategy, will be used to test the association between each individual's pre-post profile and treatment response. Moreover, we will use regression discontinuity analyses compare observations clustered closely on either side of a process-level threshold around a particular intervention. This analysis would allow us to examine the local average treatment effects on pre-post measures in a non-parametric data-driven manner.

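### The latent profile analysis tests assigned class membership against treatment response with no correction for classification error, and leaves response undefined, so the association can be biased in either direction

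*Protocol*

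**What the plan says.** Protocol Section I.13 (Statistical Considerations) compares the arms by General Linear Modeling. It then adds that "structural equation modeling (SEM) and latent profile analysis (LPA) will be used to examine variable-centered (correlation between measures) versus person-centered (profiles of individuals) alternatives". The LPA is described in one sentence: "LPA, whereby each individual is assigned to a mutually exclusive assay class (i.e. profile) based on a data-driven analytic strategy", and it "will be used to test the association between each individual's pre-post profile and treatment response". The SAP, under its heading on statistical power, data management and analysis, repeats this (each individual "is assigned to a mutually exclusive assay class (i.e. profile") and adds no detail.

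Neither document names the profile indicators, the number of classes or the rule for choosing it, a separation or entropy threshold, or the measure of treatment response. Neither mentions posterior probabilities, classification error, or a one-step or three-step model. The power statement, "A sample size of 100 will allow us to evaluate the effect of ongoing substance use as a moderator of treatment response at 80% power", concerns a different moderator. No figure is given for the LPA.

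**The concern.** A latent class is estimated, not observed. When each person is placed in the most likely class and that label is carried into a test, people placed wrongly mix the groups. Provided response is unrelated to the indicators within class, the mixing shrinks the difference between classes, and an arm-by-profile interaction shrinks in the same way.

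The choice of measures matters as much. The plan calls the profile a pre-post profile, so it appears to include post-training scores. If response is also read from those tasks, people are sorted partly on the chance variation that enters their response, and the difference can be inflated.

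The Protocol's long-term goal is to match remediation to a patient's deficits, and LPA is its person-centred analysis. An attenuated result could make a real profile difference look negligible; an inflated one could support matching on an artefact.

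**Working it through.** **The plan's figures.** There is no LPA figure to reproduce. The 80% power at N = 100 is for moderation by ongoing substance use and comes without an effect size, so it cannot be reproduced. For scale, assume two-sided alpha 0.05, 1:1 arms and a 50/50 moderator, which gives four cells of 25. The interaction has SE = sqrt(4 × 1/25) = 0.40 SD, so 80% power needs (1.960 + 0.842) × 0.40 = 1.12 SD.

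**Inputs.** From the documents: N = 100, two arms, assignment to one class, then a test. Assumed, because the documents are silent: two classes, four indicators, a true class difference of 0.60 SD in response, and D of 2.0, 2.5 or 3.0.

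**Analytic check.** With known parameters, two equal classes and response independent of the indicators within class, the misclassification rate is Φ(−D/2) and the hard-assigned difference is multiplied by 1 − 2Φ(−D/2).

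- D = 2.0: 1 − 2 × 0.159 = 0.68; 0.60 becomes 0.41
- D = 2.5: 1 − 2 × 0.106 = 0.79; 0.60 becomes 0.47
- D = 3.0: 1 − 2 × 0.067 = 0.87; 0.60 becomes 0.52

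**Simulation, classes estimated from 100 people, response separate from the indicators, true value 0.60.**

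| D | Hard-assigned estimate | 95% CI coverage | BCH-corrected median |
|---|---|---|---|
| 2.0 | 0.39 | 83% | 0.50 |
| 2.5 | 0.45 | 90% | 0.55 |
| 3.0 | 0.51 | 93% | 0.56 |

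Coverage after correction was 92% to 95%, with the same root mean squared error and power as hard assignment. In similar runs a true arm-by-profile interaction of 0.80 SD came out at about 0.50, 0.60 and 0.68.

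**Source of the undercoverage.** Mean estimated standard errors under hard assignment were 0.213, 0.206 and 0.203, against actual sampling SDs of 0.220, 0.199 and 0.206, so they are about right. Biases of 0.21, 0.15 and 0.09 alone predict coverage of Φ(1.96 − bias/SE) − Φ(−1.96 − bias/SE) = 83%, 89% and 93%. The bias therefore explains the shortfall.

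**Dependence on separation.** Runs with a 40% class share, four or six indicators and a true difference of 0.50 SD lost about 30% to 50% at entropy 0.61 to 0.69 (coverage 77% to 89%), 13% to 17% at 0.79 to 0.83, and 3% to 5% at 0.92 or above, where coverage was near nominal. At the poorest separation the corrected median was 0.34, so correction recovers only part of the loss there.

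**Response sharing variance with the indicators (within-class correlation 0.5, assumed), true value 0.60.**

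| D | Hard-assigned estimate | BCH-corrected median |
|---|---|---|
| 2.0 | 0.90 | 1.19 |
| 2.5 | 0.84 | 1.03 |
| 3.0 | 0.80 | 0.89 |

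The bias reverses, and correction moves the estimate further from the truth. With no true class difference, the second set of runs gave false-positive rates of 31%, 11% and 7% at entropy 0.79, 0.92 and 0.99. With a separate response the rate was 5% to 7%.

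**The case against.** The strongest reply is that the documents never say the class will be treated as known. Mutually exclusive classes are a feature of any LPA, the second step is not described, and the Protocol refers to procedures set out in a parent grant that is not available here. That stands as a limit: a reader might infer that the plan commits to an uncorrected test, but the text shows only assignment, then a test, with no correction described. Assign-then-test remains the natural reading, and a short addition would settle it.

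Four other inferences are tempting and not supported:

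- **That associations will be understated.** The direction depends on whether response overlaps with the indicators, which the plan leaves open.
- **That the standard errors are too small, as a second defect.** In the runs above they were about right; the coverage loss comes from the bias.
- **That N = 100 causes the attenuation.** Class separation drives it. The small sample makes the class solution and the correction less stable.
- **That the trial's main result is compromised.** The LPA is additional to the comparison of arms.

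It is also fair to say that the size is unknown, since no separation is given, and that with well-separated classes hard assignment does little harm.

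**Conclusion.** The point holds in conditional form and merits a change to the plan. As described, the profile-response test has no protection against classification error. With response separate from the indicators and D of 2.0 to 3.0, the estimate falls short by about 0.09 to 0.21 SD on a true 0.60 SD. With shared measures it can overshoot by 0.20 to 0.30 SD (0.80 to 0.90 against 0.60). All of these sizes rest on assumed class structure, separation and within-class correlation; none is a figure from the documents. What the documents do establish is that indicators, response measure and treatment of class uncertainty are unspecified, so neither the size nor the sign of the bias can be ruled out in advance.

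**What to change.** In Protocol Section I.13 and the matching SAP paragraph:

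1. Name the profile indicators, and define treatment response by a measure that is not among them. The substance use already collected at follow-up is one example. This must come first, because correction made matters worse when the two overlapped.
2. Test the profile-response association, and any arm-by-profile term, with a bias-adjusted three-step analysis (BCH or maximum likelihood) or a one-step model, with robust standard errors.
3. Report entropy and the classification table, and use hard assignment only to describe the profiles.

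The cost is a few sentences and a standard software option, with no new data. Intervals will be somewhat wider, power does not improve, and some bias remains when classes are poorly separated.
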